to Week 24 (which is beyond the primary endpoint at Week 12) will provide a background incidence in the study population for possible safety findings and will ensure a valid assessment of the durability of the treatment response. It will support a more robust characterization of the safety profile of remibrutinib, i.e., if safety events are observed in both the placebo and remibrutinib arms, it may be inferred that the events are not necessarily related to the study treatment. To limit the duration of placebo treatment, the placebo-controlled treatment period will stop at Week 24, since a period of 24 weeks allows a reliable and valid assessment of efficacy and safety in patients with CSU.

3. **Open-label treatment period:** during this treatment period of 28 weeks, all participants will receive open-label remibrutinib (25 mg b.i.d.). Together with the preceding double-blind, placebo-controlled period, a total of up to 52 weeks of remibrutinib (25 mg b.i.d.) treatment will be studied within this trial. This is in line with current CSU treatment guidelines (Zuberbier et al 2018) and will provide adequate long-term efficacy and safety data to fully characterize the value of remibrutinib (25 mg b.i.d.) in CSU treatment. Switching placebo treated participants to active treatment with remibrutinib at Week 24 gives all participants the opportunity to receive active treatment with remibrutinib within the course of this study.
4. **Follow-up period:** a treatment-free follow-up period of four weeks at the end of the study will be implemented for all participants who do not enroll into the extension study (currently in planning stage). This allows the assessment of safety of treatment discontinuation as well as the dynamics of potential re-occurrence of CSU signs and symptoms after treatment discontinuation.

The study population consists of participants with CSU (UAS7 score ≥ 16 , with HSS7 score ≥ 6 and ISS7 score ≥ 6), who have a duration of CSU of ≥ 6 months and who are inadequately controlled despite treatment with second generation H1-antihistamines at least at locally label approved dose. Importantly, patients who have inadequately responded to or did not tolerate anti-IgE biologic treatments are also eligible for this study. Thus, CSU patients with a high unmet medical need are the target population for this study.

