BTK inhibition is a new therapeutic principle for the treatment of CSU that significantly differs from currently available treatment options in terms of its mode of action and route of administration. Remibrutinib may therefore offer a treatment option for patients with contraindications against or inadequate response to approved treatment options for CSU including anti-IgE directed biologics. These patients, for whom a high unmet need for new treatments exists, are part of the eligible patient population of this study. In the above-mentioned Phase 2b trial CLOU064A2201, remibrutinib showed a rapid onset of action already after the first week of treatment, which is of significant benefit for CSU patients, who often have a high current symptom burden. Furthermore, the oral route of administration of remibrutinib offers additional convenience compared to injectable biologics.

Taken together, the benefit for study participants is that treatment with remibrutinib could substantially improve their CSU signs and symptoms and lead to a better quality of life.

The available clinical safety experience has documented favorable safety and tolerability of remibrutinib. As of 10-Mar-2022, approximately 903 participants (healthy volunteers (HVs) and patients suffering from CSU, asthma, Sjogren's Syndrome (SjS), atopic dermatitis (AD), and relapsing multiple sclerosis (RMS)) have been exposed to remibrutinib at doses ranging from 0.5 mg to 600 mg, placebo or comparator. A maximum tolerated dose has not been identified.

In the final analysis of the Phase 2b trial CLOU064A2201 in patients with CSU, 309 participants (safety set (SAF)) received remibrutinib at doses/regimens up to 100 mg b.i.d. for up to 12 weeks. Most adverse events (AEs) were mild in severity, without clustering of specific AEs and no apparent dose related pattern was identified. The most frequent adverse events were reported in the following System Organ Classes (SOC): Infections and infestations (24.0% any remibrutinib dose vs 21.4% in placebo arm), Skin and subcutaneous tissue disorders (16.9% vs 4.8%), Nervous system disorders (13.1% vs 16.7%), and Gastrointestinal disorders (11.2% vs 11.9%). The most frequent AEs (defined by MedDRA Preferred Term (PT), occurring in $\geq 5\%$ of participants in either Any remibrutinib or placebo arm) were:

- Headache: 9.7% in any remibrutinib arm vs. 14.3% in placebo arm
- Nasopharyngitis: 8.6% in any remibrutinib arm vs. 7.1% in placebo arm

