1. *Effect on platelet function - risk for bleeding:* BTK is a signaling molecule in one of several platelet activation pathways, and clinically relevant effects of remibrutinib on platelet functions were observed in the remibrutinib preclinical toxicology program. The mode of

action by which remibrutinib could potentially cause bleeding is currently not fully understood. In vitro assessments suggest a target-related impact on platelets, similar to effects induced by the BTK inhibitor ibrutinib, which has been shown to inhibit clot retraction ([Bye et al 2015](#)). Furthermore, remibrutinib inhibited collagen-induced platelet aggregation. BTK inhibition does not have any impact on the plasmatic coagulation system and, plasmatic coagulation was not affected in the human Phase 1 study up to the highest dose of 600 mg remibrutinib. In CSU, in the completed core CLOU064A2201 Phase 2b study, 18 (6.7%) non-serious bleeding events were reported in any remibrutinib arm compared to one event on placebo (2.4%); none of the AEs was serious or severe. All the bleeding AEs events reported were mild, except 2 moderate AEs: gingival bleeding and hematuria. Two bleeding events (petechiae and hematuria) led to study treatment discontinuation. There were no notable clinically relevant abnormalities for coagulation parameters, hemoglobin levels and platelet counts noted in these studies. In the interim analysis of the open-label long-term (up to 52 weeks) extension trial CLOU064A2201E1, the rate of bleeding events (4.4%) was comparable to that seen in the core trial; all events were non-serious, all but 2 events (the purpura and heavy menstrual bleeding in the setting of leiomyoma) were mild in severity. Potential effects of remibrutinib on hemostasis should be monitored both clinically and by standard, validated laboratory measures including complete blood count and standard coagulation parameters. Clinical monitoring should focus on skin (bruising, petechiae) and mucosa (e.g., gastro-intestinal (GI) tract bleeding including gingival, rectal, and conjunctival bleeding). i.e., Patients with a known history of bleeding disorders, or with a history of clinically relevant gastrointestinal bleeding and patients requiring anti-platelet or anticoagulant therapy (other than aspirin up to 100 mg/d or clopidogrel up to 75 mg/d) are excluded from the trial; the use of dual anti-platelet therapy (e.g., acetylsalicylic acid + clopidogrel) is prohibited (see details in [Section 5.2](#) and [Section 6.2.3](#)). In case of a significant bleeding event, study treatment must be discontinued immediately. Please, refer to the current IB for further details.

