12.8 Sample size calculation

12.8.1 Primary endpoint(s)

In order to fulfill registration and ICH E1 requirements on the number of participants treated for 6 months and 12 months in the development program, a sample size of 300 participants in the active arm and 150 in the placebo arm is targeted. Hence, the total sample size is 450 randomized participants.

From an efficacy point of view, the sample size justification is based on UAS7 change from baseline (for scenario with one primary endpoint), ISS7 and HSS7 change from baseline (for scenario with co-primary endpoints) and achievement of $UAS7 \leq 6$ and $UAS7 = 0$ at Week 12. To avoid assigning an unnecessary large number of participants to placebo, participants will be randomized in a 2:1 ratio to remibrutinib 25 mg b.i.d. and placebo arms, respectively.

[REDACTED]

All calculations were performed with nQuery Advisor 8.4.1.0 and Ri386 4.0.2 softwares.

For scenario with UAS7 as the primary efficacy endpoint

UAS7 change from baseline at Week 12

Approximately 10% drop-out is expected at week 12, thus with 270 participants in the active arm and 135 participants in the placebo arm, this gives a nominal power of more than > 99% to detect a difference between remibrutinib and placebo if the mean change of UAS7 from baseline to Week 12 is at least 10 in favor of remibrutinib, with common standard deviation of approximately 12 (based on the primary endpoint analysis of Phase 2b study (CLOU064A2201)), based on a t-test, assuming type I error 0.025 (one-sided).

For scenario with ISS7/HSS7 as the co-primary efficacy endpoints

ISS7 change from baseline at Week 12

Approximately 10% drop-out is expected at week 12, thus with 270 participants in the active arm and 135 participants in the placebo arm, this gives a nominal power of more than > 99% to detect a difference between remibrutinib and placebo if the mean change of ISS7 from baseline to Week 12 is at least 4 in favor of remibrutinib, with common standard deviation of approximately 6 (based on the primary endpoint analysis of Phase 2b study (CLOU064A2201)), based on a t-test, assuming type I error 0.025 (one-sided).

HSS7 change from baseline at Week 12

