2.7.1 Adverse events (AEs)

All information obtained on adverse events will be listed by treatment group and participant.

The number (and percentage) of participants with treatment emergent adverse events (the events which occurred during the on-treatment period, TEAE) will be summarized by study period in the following ways:

- by treatment group, primary system organ class and preferred term.
- by treatment group, primary system organ class, preferred term and maximum severity.
- by treatment group, Standardized MedDRA Query (SMQ, narrow) and preferred term.

Separate summaries will be provided for study medication related adverse events, death, serious adverse events, other significant adverse events leading to discontinuation by study period and treatment group.

The most common adverse events reported ($\geq 3\%$ in any group for each preferred term in the SOC-PT table or $\geq 3\%$ in any group for each SMQ table) will be presented in descending frequency according to its incidence in LOU064A 25mg bid starting from the most common event. The cut-off of 3% can be re-evaluated based on number of participants and events.

In these summary tables, a participant with multiple adverse events within a primary system organ class is only counted once towards the total of the primary system organ class.

In the summary of AEs by severity, if a participant reported more than one adverse event with the same preferred term, the adverse event with the greatest severity will be presented. If a participant reported more than one adverse event within the same primary system organ class, the participant will be counted only once with the greatest severity at the system organ class level.

In addition, for adverse events and serious adverse events, exposure adjusted incidence rates will be estimated by treatment group for the double-blind period and for the entire study period. The rate estimates will be reported with exact Poisson 95% CIs (Garwood 1936, Sahai and Khurshid 1993). Please see [Section 5.4.2.4](#) for details.

For infections and infestations (SOC), the number (and percentage) of participants with this event will be summarized by treatment group, SOC, HLGT, HLT and PT for the double-blind period and the entire study period.

[Table 2-13](#) presents overview of analyses on TEAEs.

Table 2-13 Overview of safety analyses on TEAEs

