2.7.1.1 Adverse events of special interest / grouping of AEs

Adverse events of special interest (AESI) for remibrutinib (such as risks defined in the Safety Profiling Plan, Risk Management Plan or topics of interest regarding signal detection or routine analysis) will be defined based on the latest Case Retrieval Strategy (eCRS). The comprehensive search of AESI will be performed for all TEAEs.

The number (and percentage) of participants with AESI will be summarized by safety topic of interest (i.e. risk name) and PT for study period and treatment group. Exposure adjusted incidence rate will also be provided by treatment group for the double-blind period and the entire study period.

In addition, for the selected AESIs (Infections, Bleeding, Cytopenias), the number of AESI events will be summarized by safety topic of interest (i.e., risk name) for study period and treatment group.

Summaries will also include the exposure adjusted occurrence rate and the corresponding 95% CI, the number of events per participant, time to onset of first event, duration of the events, the severity of the events, the outcome of events, treatment related events, the action taken with the study treatment for each event and duration of study drug interruption for events leading to study drug interruption.

- Exposure Adjusted Occurrence Rate (EAOR) will be calculated as follows:

EAOR = $100 * \text{total number of events} / \text{total exposure subject-time (years)}$

The exact Poisson 95% CIs (Garwood 1936, Sahai and Khurshid 1993) will be used. Please see [Section 5.4.2.5](#) for details.

For duration of study drug interruption (in days), once the events leading to study drug interruption are selected, the drug interruption occurred within 7 days of the event onset date will be considered. If there are more than one interruption, only the first interruption will be considered.

For the selected AESIs (Infections, Bleeding, Cytopenias), during the double-blind period, the number of events (per risk name), EAOR, and number of participants at risk occurring between 0-≤4 weeks, 4-≤12 weeks, 12-<24 weeks will be displayed by treatment group.

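### For events that are not rare, occurrence in both arms says nothing about relatedness, and the readable SAP defines no between-arm safety estimate to use instead

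*Protocol*

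**What the plan says.** Protocol 4.1 justifies placebo control to Week 24, beyond the Week 12 endpoint, partly on safety grounds: it supplies a background incidence and a safety assessment against placebo. It then spells out the reasoning: "if safety events are observed in both the placebo and remibrutinib arms, it may be inferred that the events are not necessarily related". The sentence concerns relatedness to treatment and mentions no frequency, difference or threshold.

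SAP 2.1.1.1 describes the double-blind safety analysis as a comparison of LOU064 with placebo up to Week 24. What is specified is by arm. For AEs and SAEs, SAP 2.7.1 states that "exposure adjusted incidence rates will be estimated by treatment group for the double-blind period and for the entire study period", with exact Poisson intervals. For AESIs, SAP 2.7.1.1 states that "Exposure adjusted incidence rate will also be provided by treatment group for the double-blind period and the entire study period". For infections, bleeding and cytopenias it adds event counts and the exposure-adjusted occurrence rate (EAOR) with its CI. Table 2-13 lists crude incidence and the exposure-adjusted incidence rate (EAIR) by group. For AEs leading to discontinuation it lists crude incidence only.

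The interval methods in SAP 5.4.2.4 to 5.4.2.6 are all for a single rate or proportion. The treatment difference with a CI for binary data (SAP 2.5.2.6 and 5.4.2.2) is set out for the efficacy responder endpoints.

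**The concern.** An event with any appreciable background rate will turn up in a placebo arm of 150 whatever the drug does. Seeing it in both arms therefore cannot separate a harmful drug from a harmless one. The information lies in how much more often it occurs on remibrutinib and how precisely that is known, and this is the quantity for which the SAP defines no estimator.

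Safety and tolerability are a listed secondary objective in both endpoint scenarios, and the risks singled out in SAP 2.7.1.1 (infections, bleeding, cytopenias) all plausibly occur on placebo. If the comparison that helps to justify 24 weeks of placebo is left to the reader's eye, its size and uncertainty go unreported.

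**Working it through.** **Inputs.** Arm sizes come from protocol 12.8.1: "a sample size of 300 participants in the active arm and 150 in the placebo arm is targeted". The same section gives the sizes after dropout: "Approximately 10% drop-out is expected at week 12, thus with 270 participants in the active arm and 135 participants in the placebo arm". The illustrative rates are the Phase 2b bleeding figures in protocol 4.5: "18 (6.7%) non-serious bleeding events were reported in any remibrutinib arm compared to one event on placebo (2.4", the last figure being a percentage.

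**Reproducing the Phase 2b percentages.** Protocol 4.5 says "309 participants (safety set (SAF)) received remibrutinib at doses/regimens up to 100 mg b.i.d. for up to 12 weeks". If all 309 had received remibrutinib, 18/309 would be 5.8%, not 6.7%, so the 309 must include placebo. The placebo denominator is not stated. A value of 42 fits both figures (41 also fits): 1/42 = 2.4% and 18/267 = 6.7%, a ratio of 2.83. The 95% CI for that ratio is about 0.4 to 20.7, because it rests on one placebo event. The rates are therefore illustrative only, and I treat events as participants.

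**Probability that an event is seen in both arms.** With placebo rate p and risk ratio RR:

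P(both) = [1 − (1 − p)^150] × [1 − (1 − RR·p)^300]

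For p = 2.4%, the placebo term is 1 − 0.976^150 = 0.974. The remibrutinib term is 0.999 at RR = 1 and effectively 1 at RR = 2.8 or 4.

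| Placebo rate | RR = 1 | RR = 2.8 | RR = 4 |
|---|---|---|---|
| 2.4% | 0.973 | 0.974 | 0.974 |
| 1% | 0.740 | 0.778 | 0.779 |
| 0.5% | 0.411 | 0.521 | 0.527 |
| 0.1% | 0.036 | 0.079 | 0.098 |

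At 270 vs 135 the 2.4% row gives 0.961 at RR = 1 and 0.962 at RR = 2.8. If the bleeding rates doubled over 24 weeks (an assumption), the probability would be 0.999. For a fixed placebo rate the probability can only rise with RR, because only the remibrutinib term changes. Occurrence in both arms is therefore never evidence against a drug effect on this calculation. For rarer events it points weakly the other way.

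**What a between-arm estimate would show.** If 6.7% vs 2.4% recurred at 300 vs 150, the expected counts are 300 × 0.067 = 20.1 and 150 × 0.024 = 3.6.

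- Risk difference: 4.3 points. Its large-sample SE is √(0.067 × 0.933/300 + 0.024 × 0.976/150) = 0.0191, so the 95% CI is 4.3 ± 3.7, or 0.6 to 8.0 points.
- Risk ratio: 2.8. The SE of its log is √(0.933/20.1 + 0.976/3.6) = 0.563, so the 95% CI is 0.9 to 8.4.
- Newcombe interval with whole counts, 20/300 vs 4/150: the Wilson limits are 4.36% to 10.07% and 1.04% to 6.66%. The difference is 4.0 points, with lower limit 4.0 − √(2.31² + 3.99²) = −0.6 and upper limit 4.0 + √(3.41² + 1.62²) = 7.8.

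By exact enumeration of the two binomials at these rates, the Newcombe interval lies wholly above 0 in 46.8% of trials of this size. With equal 2.4% rates it does so in 1.1%. Unlike occurrence in both arms, it responds to the drug effect. Its width also shows how little a single study settles.

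**The case against.** The strongest reply is that 4.1 contains no decision rule. The sentence is hedged twice, has no threshold, and no SAP section uses it. Its literal content is also true: an event seen on placebo can occur without the drug. The protocol does not follow the crude reading itself. Bleeding occurred in both Phase 2b arms, yet 4.5 quotes the two rates, lists bleeding as a potential risk and provides for monitoring. Infections are likewise read by rate, 24.0% vs 21.4%. The SAP gives bleeding extra analyses as a selected AESI. All of this stands.

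Three stronger conclusions that a reader might draw are therefore not supported.

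- That the trial would dismiss a real excess of bleeding about 97% of the time. The 0.97 describes how uninformative the reasoning is, not how often a planned procedure errs. It applies only to events about as common as grouped bleeding.
- That safety will be judged by whether the per-arm intervals overlap. Neither document says so. Overlap would be insensitive (at 6.7% vs 2.4% the per-arm 95% intervals separate in only 12.5% to 15.4% of trials of this size), but nobody has proposed it.
- That no between-arm safety estimate exists anywhere in the programme. The SAP cites a master analysis plan and a separate DMC analysis plan, which are not available here. The absence is shown only for the readable text of this SAP.

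It can also be said that any reader can derive a difference from the tabulated counts. That is true for the point estimate. Prespecifying the estimator and its interval is still better than leaving each reader to choose.

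**Conclusion.** The point holds as a modest one. The reasoning in 4.1 carries no information about relatedness for events that are not rare: about 0.97 at a 2.4% placebo rate whether the risk ratio is 1 or 4. It carries little at 1% (0.74 to 0.78) or 0.5% (0.41 to 0.53). The readable SAP calls the double-blind safety analysis a comparison but defines no difference or ratio with a CI for any safety endpoint.

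The figures assume independent participants, full arm sizes of 300 and 150, and events counted as participants. The 2.4% and 6.7% come from pooled doses over up to 12 weeks with a single placebo event, so near-tripling is an illustration, not a forecast. The conclusion that occurrence in both arms does not discriminate does not depend on those rates being right. This is a cheap improvement to the reporting, not an error that invalidates a planned analysis.

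**What to change.** In SAP 2.7.1, 2.7.1.1 and the double-blind row of Table 2-13, add the risk difference, remibrutinib minus placebo, with a 95% CI (for example Newcombe or Miettinen-Nurminen). Do this for SAEs, AEs leading to discontinuation and each AESI risk name. Optionally add the EAIR difference or ratio with a 95% CI. Label these descriptive, give no p-values, and read the estimate with its whole interval. No margin is defined, so neither limit should act as a criterion by itself.

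At the next protocol amendment, reword the sentence in 4.1 to say that relatedness at group level is judged from the difference in incidence between arms in the double-blind period, and that occurrence in both arms is not by itself evidence against a relationship.

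The cost is a few columns computed from counts already tabulated, with no new data. Several unadjusted intervals will be shown and some will exclude 0 by chance. Table 2-13 has a double-blind row only at the primary analysis, and the latest SAP amendment is dated before the final analysis. If the primary analysis has already been run, the added estimates should be marked as specified afterwards. The protocol wording needs the usual amendment approvals, so it is not worth an amendment of its own.

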4.1.1 Rationale for choice of background therapy

Second-generation H1-antihistamines are chosen as background medication. Considering the add-on remibrutinib therapy, this reflects the current treatment guidelines, which recommend to add a second or third-line therapy to H1-antihistamine background therapy in CSU patients who are not adequately controlled by H1-antihistamines (Zuberbier et al 2018). Furthermore, it allows active treatment of participants in the placebo arm, including the use of additional rescue medication. Thus, participants in the placebo arm are not left without CSU treatment.

